## 4. Treatments

### 4.1 Composition, Formulation, and Storage

At study sites, all study medication will be stored as described in the pharmacy manual and inventoried in accordance with applicable state and federal regulations.

#### Investigational Treatment

Chemical Name:      Chemical Name: *N*-{4-[(6,7-dimethoxyquinolin-4-yl)oxy]phenyl}-*N'*-(4-fluorophenyl)cyclopropane-1,1-dicarboxamide, (2*S*)-hydroxybutanedioate

#### Cabozantinib Tablets

Exelixis internal number: XL184

Cabozantinib tablets are supplied as film coated tablets containing cabozantinib malate equivalent to 20 mg and 60mg of cabozantinib and contain microcrystalline cellulose, lactose anhydrous, hydroxypropyl cellulose, croscarmellose sodium, colloidal silicon dioxide, magnesium stearate and Opadry® yellow. All tablet strengths are prepared from a common blend and are distinguished by shape. The 20 mg tablets are round and the 60 mg tablets have an oval shape. The components of the tablets are listed in Table 4-1.

TABLE 4-1: CABOZANTINIB TABLET COMPONENTS AND COMPOSITION

Ingredient	Function	% w/w
Cabozantinib malate (25% drug load as cabozantinib)	Active Ingredient	31.7
Microcrystalline Cellulose (Avicel PH-102)	Filler	38.9
Lactose Anhydrous (60M)	Filler	19.4
Hydroxypropyl Cellulose (EXF)	Binder	3.0
Croscarmellose Sodium (Ac-Di-Sol)	Disenegrant	6.0
Colloidal Silicon Dioxide,	Glidant	0.3
Magnesium Stearate	Lubricant	0.75
Opadry Yellow Film Coating which includes:		
- HPMC 2910/Hypromellose 6 cp		
- Titanium dioxide	Film Coating	4.00
- Triacetin		
- Iron Oxide Yellow		

#### 4.2 Dose, Schedule and Route

Study medication will be taken daily at a dose of 40 mg/m^2. Drug cycles will last 28 days and be continuous for up to 12 months of therapy on study.

Cabozantinib will be held for subjects who experience toxicity until the toxicity has decreased to grade 1. Cabozantinib will then be reduced by one dose level and not re-escalated in subsequent cycles. Subjects who experience toxicity at dose level -1 will be off study (See Section 7.0 for Dose Modification guidelines).

Dose Level	Dose (mg/m  /dose with max dose 60 mg/day)
-1	30 mg/m 
1	40 mg/m 

Actual dosing will be based on dosing nomogram in Appendix VI

Cabozantinib must be taken on an empty stomach. Subjects must be instructed not to eat for at least 2 hours before and at least 1 hour after taking cabozantinib. Subjects should be instructed to take their cabozantinib dose at approximately the same time every day. If a subject misses a dose, the dose may be taken later only if it is within 12 hours of when the missed dose should have been taken. The missed dose should not be made up if it is within 12 hours of the next scheduled dose.

Cabozantinib tablets should be swallowed whole with at least 8 ounces of water. The tablets should not be crushed. Grapefruit, grapefruit juice, Seville oranges and their products should be avoided by subjects taking cabozantinib.

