## 7. Study Procedures

**Pre-study evaluations:** The investigational nature and objectives of the trial, the procedures and treatments involved and their attendant risks and discomforts and potential alternative therapies will be carefully explained to the patient and or the patient's parent(s) or guardian if the patient is a child, and a signed informed consent and assent will be obtained according to institutional and federal guidelines.

Diagnostic or laboratory studies performed exclusively to determine eligibility for this trial must only be done after obtaining written informed consent. Documentation of the informed consent for screening will be maintained in the subject's research chart. Studies or procedures that were performed for clinical indications (not exclusively to determine eligibility) may be used for baseline values even if the studies were done before informed consent was obtained.

Within 14 days of starting study drug, pre-study evaluations include: History and physical exam, laboratory studies, performance status, pregnancy test (for females of child bearing age), 12-lead ECG and MRI of brain +/- spinal cord.

**Criteria for Starting Subsequent cycles:** A cycle may be repeated every 28 days(+/- 3 days) if the subject does not have evidence of progressive disease and has again met laboratory parameters as defined in the eligibility criteria, with the exception of ANC, which must be  $\geq 1000/\text{mm}^3$  to start each cycle.

History and physical exam, laboratory studies, performance status, study drug and corticosteroid drug diaries will be collected every 15 days (+/- 72 hours) after initiation of drug for cycles 1-3.

History and physical exam, laboratory studies, performance status, study drug and corticosteroid drug diaries will be collected every 28 days (+/- 72 hours) for cycles 4-12.

MRI's will be performed every 3 months (+/- 1 week).

12-lead ECG will be performed at pre-study, End of Cycle 1, End of Cycle 3 and End of Cycle 6, unless additional ECGs are required per protocol guidance (dose modification or concomitant medication usage)

Study Schedule: STUDIES TO BE OBTAINED	Pre-Study 	Cycle 1 ^	Cycle 2, 3 ^	Cycle 4-12 ^	Completion of Study
Informed Consent obtained	X				
History (including Con Meds)	X	Day 28	Days 15, 28	Day 28	X
Physical exam with vital signs and pulse ox	X	Days 15 and 28	Days 15, 28	Day 28	X
Height, weight, BSA	X	Day 28	Days 15, 28	Day 28	X

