## 7.1 Dose Modifications

### Dose Modifications of Cabozantinib for Treatment-Related AEs

CTCAE v.5.0 Grade	Recommended Guidelines for Management a
Grade 1 AEs	Add supportive care as indicated. Continue cabozantinib treatment at the current dose level if AE is manageable and tolerable.
Grade 2 AEs which are tolerable and are easily managed	Continue cabozantinib treatment at the current dose level with supportive care.
Grade 2 AEs which are intolerable and cannot be adequately managed	At the discretion of the investigator, cabozantinib should be dose reduced or interrupted.  Note: It is recommended that dose holds be as brief as possible.
Grade 3 AEs (except clinically non-relevant laboratory abnormalities)	Cabozantinib should be interrupted unless the toxicity can be easily managed with a dose reduction and optimal medical care.  Note: It is recommended that dose holds be as brief as possible.
Grade 4 AEs (except clinically non-relevant laboratory abnormalities)	Subjects should have cabozantinib interrupted immediately. Discontinue cabozantinib unless the following criteria are met: 
 
• Subject is deriving clear clinical benefit as determined by the investigator and agreed by the Sponsor
 
• Toxicity can be managed with a dose reduction following recovery to Grade 1 (or baseline) and optimal medical care
 

AE, adverse event.

Note: The dose delay and modification criteria for specific medical conditions are provided below.

a Study treatment dose adjustment is only needed if the toxicity was deemed related to cabozantinib treatment or had an unclear relationship to cabozantinib treatment.

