**Dose Modifications for Hematologic toxicity**

If a patient experiences dose-limiting Grade 4 neutropenia or thrombocytopenia, the treatment will be withheld. Counts should be checked every 3 - 4 days for thrombocytopenia and every other day for neutropenia during this time. If the toxicity resolves to meet eligibility parameters within 14 days of drug interruption, the patient may resume treatment at the next lower dose level. Doses reduced for toxicity will not be re-escalated, even if there is minimal or no toxicity with the reduced dose.

If dose-limiting toxicity does not resolve to meet eligibility or baseline parameters within 14 days of drug interruption, the patient must be removed from protocol therapy.

One dose reduction will be allowed for toxicity. If a patient does not tolerate reduced dose, they must be removed from protocol therapy.

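### Section 4.2 orders a hold, a lasting reduction and, at level -1, removal for unqualified toxicity; Section 7 treats through some of the same events, and the text does not say which governs

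*Combined protocol and SAP*

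**What the plan says.** Section 4.2 gives three instructions in sequence. The first is "Cabozantinib will be held for subjects who experience toxicity until the toxicity has decreased to grade 1". The second is "Cabozantinib will then be reduced by one dose level and not re-escalated in subsequent cycles". The third, with the only cross-reference, is "Subjects who experience toxicity at dose level -1 will be off study (See Section 7.0 for Dose Modification guidelines". The paragraph does not ask whether the toxicity is related to the drug or tolerable.

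The general table in Section 7.1 grades the response. For Grade 2 events that are tolerable and readily managed it says "Continue cabozantinib treatment at the current dose level with supportive care". For Grade 3 events it says "Cabozantinib should be interrupted unless the toxicity can be easily managed with a dose reduction and optimal medical care". Its footnote adds "Study treatment dose adjustment is only needed if the toxicity was deemed related to cabozantinib treatment or had an unclear relationship to cabozantinib treatment".

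The condition-specific rules in Section 7 follow the same pattern. Tolerated Grade 2 palmar-plantar erythrodysesthesia (PPE) may continue on treatment. So may Grade 2 hypothyroidism that is adequately replaced (Section 7.2). The proteinuria table allows a hold and restart when protein remains high after a dose reduction. The liver rule discontinues at the lowest dose level only for recurrent drug-related elevations of Grade 3 or higher.

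On removal after the single permitted reduction, the hematologic subsection of 7.1 says "If a patient does not tolerate reduced dose, they must be removed from protocol therapy". The non-hematologic subsection has no matching sentence.

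**The concern.** The same event can lead to different actions depending on the section consulted. Followed literally, 4.2 would permanently lower a child's dose, or end participation at level -1, for an event that Section 7 keeps on treatment.

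The two primary aims are safety and tolerability, and disease control including stable disease of at least 6 months. The rule that produces reductions and removals bears directly on what the trial observes for both. Section 14.3.3 also excludes patients with significant protocol violations from the efficacy population. With two unreconciled rules, following one can look like a departure from the other.

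The terms differ as well. Section 4.2 takes the subject off study, whereas the hematologic subsection removes the patient from protocol therapy. Overall survival to 12 months is a secondary aim, and 4.2 does not say whether follow-up continues.

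**Working it through.** No arithmetic decides this point, so the rules are set side by side.

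**Step 1: scope of 4.2.** The hold lasts until the toxicity falls to grade 1, so the hold and the reduction that follows concern events above grade 1. The level -1 sentence carries no such limit and, as written, applies to any toxicity.

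**Step 2: same event, two instructions.**

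| Event | Section 4.2 read literally | Section 7 |
|---|---|---|
| At 40 mg/m²: related Grade 2 event, tolerable and readily managed | Hold, then 30 mg/m² permanently | Stay at 40 mg/m² (7.1 table) |
| At 40 mg/m²: Grade 2 PPE, tolerated | Hold, then 30 mg/m² | May continue (7.1, PPE) |
| At 40 mg/m²: Grade 2 hypothyroidism, replaced | Hold, then 30 mg/m² | May continue (7.2) |
| At 40 mg/m²: related Grade 3 event readily managed by reduction | Hold first, then reduce | Reduce; no hold needed (7.1 table) |
| At 40 mg/m²: event above grade 1, clearly unrelated | Hold, then reduce | No adjustment needed (7.1 footnote) |
| At 30 mg/m²: related Grade 2 event, tolerable and readily managed | Off study | Stay at 30 mg/m² (7.1 table) |
| At 30 mg/m²: protein/creatinine ratio still above 2 mg/mg after the reduction | Off study | Consider a hold until below 2 mg/mg, then restart (7.1, proteinuria) |
| At 30 mg/m²: drug-related Grade 2 ALT, AST or bilirubin elevation | Off study | Discontinuation at this level is reserved for recurrent Grade 3 or higher (7.1, liver) |

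**Step 3: precedence.** The link in 4.2 is a bare reference to Section 7.0. Section 4.2 is phrased as mandatory, while the 7.1 table presents its entries as recommended guidelines. No statement of which prevails was found elsewhere in the document.

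**Step 4: where the sections agree.** Both bar re-escalation. The dose table in 4.2 lists only one lower level, and the hematologic subsection of 7.1 allows one reduction. One sentence in the Warnings and Precautions part of 7.1 is out of line: it accepts reductions of more than one level, although only one lower level exists.

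**Step 5: laboratory events.** The gap is narrower here. Section 7 lets a new cycle start only if the subject has "again met laboratory parameters as defined in the eligibility criteria". For ALT the limit is 110 U/L against a stated upper limit of normal of 45 U/L, and 110 / 45 = 2.44 times that limit. This can delay a cycle, but it does not by itself require a permanent reduction or removal, so it does not reconcile the two sections.

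**The case against.** The best reply is that 4.2 is a short summary ending in a pointer to Section 7, where 7.1 sets out detailed rules by grade and condition. A sensible site would follow the detail. The trial also has one enrolling centre, 11 planned patients and weekly safety meetings that include the principal investigator, so divergent practice is unlikely. Most of this stands: Section 7 is the likely operative rule and the practical risk is modest. It does not settle the text, because the pointer does not say that Section 7 overrides the mandatory wording in 4.2. Nor can Section 7 simply replace 4.2, since its removal rule after one reduction sits under the hematologic heading.

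Three stronger readings are tempting, and the documents do not support them.

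- **Dose loss.** A reader might infer that the conflict costs 25% to 40% of the weekly dose. Appendix VI does give (160 - 120) / 160 = 25.0% and (100 - 60) / 100 = 40.0% at its extremes. That is the size of one planned reduction under either section, not a measure of the inconsistency.
- **Blood pressure.** A reader might add readings 11 to 25 mm Hg above the 95th percentile, which Arm 3 of the hypertension algorithm treats at an unchanged dose. The documents do not show that such readings exceed grade 1, so the example does not establish a conflict over the hold and reduction.
- **Disease control.** A reader might infer a shift in the disease control rate. The documents do not show how a lower dose would change it, or how many patients would be affected.

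**Conclusion.** The inconsistency is real and should be corrected. For the hold and reduction it is confined to events above grade 1, in practice Grade 2 and manageable Grade 3 events, together with events unrelated to the drug. At level -1 it extends to any toxicity, because 4.2 sets no threshold there while Section 7 continues, interrupts or restarts treatment in some cases. No effect size is claimed.

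The conclusion rests on reading *toxicity* in 4.2 in its ordinary sense, since that paragraph does not define it. It also takes the proteinuria restart at a reduced dose to mean level -1 once that level has been reached, there being no lower one. If the sponsor already treats Section 7 as governing, the defect is one of wording, and the correction records existing practice.

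**What to change.** Replace the toxicity paragraph in Section 4.2 with:

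> Cabozantinib will be held, reduced, restarted or discontinued for toxicity related, or of unclear relationship, to cabozantinib as specified in Section 7, which governs. One reduction (40 to 30 mg/m²) is permitted, without re-escalation. Subjects at dose level -1 whose hematologic or non-hematologic toxicity cannot be managed by the interruption or supportive care that Section 7 allows, and who would need a further reduction, will be removed from protocol therapy and remain in follow-up for progression and survival.

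Also delete the sentence in the Warnings and Precautions part of Section 7.1 that accepts reductions of more than one level.

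The last sentence of the new paragraph extends the removal rule to non-hematologic toxicity. It ties removal to the need for a further reduction after the permitted measures fail. A rule removing everyone who again met a criterion for reduction would go too far, because Section 7 offers interruption as an alternative for some events and only asks that reduction be considered for lasting Grade 2 liver elevations.

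The cost is one paragraph and one deleted sentence, with the IRB review that Section 15.1.3 requires for any modification. Visits, endpoints and analysis do not change.

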## 5. Inclusion/Exclusion Criteria

### **Inclusion Criteria**

1. Age: Patients must be  $\geq 2$  years and  $\leq 21$  years of age
2. Diagnosis: Patients with relapsed or refractory central nervous system tumors. Patients must have had histologic verification of malignancy at original diagnosis or relapse. Metastatic disease to the spine or primary tumors in the spine are eligible. Patients may be in first, second, or third relapse. Subjects with intrinsic brain stem gliomas may be eligible with or without histological confirmation. Please contact study chair prior to enrollment.
3. Disease Status: Patients must have measurable disease. Linear enhancement of leptomeningeal without measurable mass is excluded.
4. Therapeutic Options: Patient's current disease state must be one for which there is no accepted standard therapy, no known curative therapy or therapy proven to prolong survival with an acceptable quality of life. For patients in whom surgery is feasible, maximal surgical resection must have occurred.
5. Performance Level: Karnofsky  $\geq 50\%$  for patients  $> 16$  years of age and Lansky  $\geq 50$  for patients  $\leq 16$  years of age (See Appendix I). Note: Neurologic deficits in patients must have been relatively stable for at least 7 days prior to study enrollment. Patients who are unable to walk because of paralysis, but who are in a wheelchair, will be considered ambulatory for the purpose of assessing the performance score.
6. Subjects must have a reasonable life expectancy of at least 2 months.
7. Prior Therapy
  - a. Patients must have fully recovered from the acute toxic effects of all prior anti-cancer chemotherapy

- i. Cytotoxic chemotherapy (including investigational agents) or biologic agents (eg. Cytokines or antibodies): At least 3 weeks after the last dose.
- ii. Nitrosoureas/mitomycin C: At least 6 weeks from the last dose.
- iii. XRT: At least 14 days after local palliative XRT (small port); At least 150 days must have elapsed if prior TBI, craniospinal XRT or if  $\geq 50\%$  radiation of pelvis; At least 42 days must have elapsed if other substantial BM radiation. e.g. Stem cell Infusion without TBI: No evidence of active graft vs. host disease and at least 56 days must have elapsed after transplant or stem cell infusion.

8. Organ Function Requirements:

- a. Adequate bone marrow function defined as: absolute neutrophil count (ANC  $\geq 1000/\text{mm}^3$ )
  - i. Platelet count  $\geq 100,000/\text{mm}^3$  (transfusion independent, defined as not receiving platelet transfusions for at least 7 days prior to enrollment)
  - ii. Patients with bone marrow metastatic disease will not be eligible.
- b. Adequate renal function defined as:
  - i. Creatinine clearance or radioisotope GFR  $\geq 70\text{mL}/\text{min}/1.73\text{ m}^2$  **or** a serum creatinine based on age/gender as follows:

Age	Maximum Serum	
	Male	Female
2 to < 6 years	0.8	0.8
6 to < 10 years	1	1
10 to < 13 years	1.2	1.2
13 to < 16 years	1.5	1.4
$\geq 16$ years	1.7	1.4

The threshold creatinine values in this table were derived from the Schwartz formula for estimating GFR (Schwartz et al. J. Peds, 106:522, 1985) utilizing child length and stature data published by the CDC.

- ii. Urine protein:  $\leq 30\text{ mg}/\text{dL}$  in urinalysis or  $\leq 1+$  on dipstick, unless quantitative protein is  $< 1000\text{ mg}$  in a 24 hour urine sample.
- c. Adequate Liver Function Defined as:

- i. Bilirubin (sum of conjugated + unconjugated)  $\leq 1.5 \times$  upper limit of normal (ULN) for age
    - ii. SGPT (ALT)  $\leq 110$  U/L. For the purpose of this study, the ULN for SGPT is 45 U/L.
    - iii. Serum albumin  $\geq 2.8$  g/dL.
  - d. Adequate coagulation status defined as: PT and INR  $\leq 1.5 \times$  ULN
  - e. Adequate pancreatic function defined as: Serum amylase and lipase  $\leq 1.5 \times$  ULN
  - f. Adequate blood pressure control defined as: A blood pressure (BP)  $\leq$  the 95th percentile for age, height and gender (Appendix II) despite optimal antihypertensive treatment within 7 days of the first dose of the study treatment. Please note that 3 serial blood pressures should be obtained and averaged to determine baseline BP.
  - g. Central nervous system function defined as: Patients with seizure disorder may be enrolled if receiving non-enzyme inducing anticonvulsants and well controlled. See Appendix III for a list of recommended non-enzyme inducing anticonvulsants.
  - h. Adequate cardiac function defined as:
    - i. No history of congenital QTc syndrome, NYHA Class III or IV congestive heart failure (CHF)
    - ii. No clinical significant cardiac arrhythmias, stroke or myocardial infarction within 6 months prior to enrollment
    - iii. QTc  
 $\leq 480$  msec. Note: One ECG must be performed for eligibility determination. If the QTc is  $> 480$  msec, two additional ECGs must be performed and the average of the three ECGs will be used to determine eligibility. Patients with Grade 1 prolonged QTc (450-480 msec) at the time of study enrollment should have correctable causes of prolonged QTc addressed if possible (i.e. electrolytes, medications). See Appendix IV for a list of drugs that prolong QTc.
9. Informed consent: All patients and/or their parents or legally authorized representatives must sign a written informed consent. Assent, when appropriate will be obtained according to institutional guidelines.
10. Archival tumor tissue slides must be sent or available, except for patients with intrinsic pontine glioma meeting the remainder of the inclusion criteria.

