## 2. Background and Rationale

[figure not shown]
Children with high grade gliomas including glioblastoma multiforme (GBM) and anaplastic astrocytoma (AA), have expected overall survival rates less than 35% despite our best available therapies. Numerous other histologic subtypes of pediatric central nervous system tumors have worse overall survival at recurrent. Additionally, most recurrent pediatric CNS tumors are characterized by aggressive clinical behavior. High grade gliomas are classified by the World Health Organization (WHO) as either grade III or IV meaning that they are highly malignant tumors with characteristic findings such as hypercellularity, nuclear atypia, and high mitotic activity with or without microvascular proliferation and pseudopalisading necrosis. High-grade gliomas include a variety of heterogeneous tumors with differing histologies, but the most common histologies are anaplastic astrocytoma and glioblastoma multiforme. Although there truly is no one accepted standard of care and treatment algorithms can vary, most experts agree that a gross total resection (GTR) followed by focal irradiation to the tumor bed plus additional

V 5.0 March 5, 2021 IUSCC-0601

chemotherapy is an appropriate treatment approach. However, with such an approach, Progression Free Survival (PFS) in patients with GTR is 35% compared to 17% with subtotal resection of tumor. Patients with recurrent disease approach mortality rates of 100%. Therefore, much work remains to be done to improve survival in these patients.

Other histologic subtypes of aggressive childhood brain tumors follow a similar pattern to high grade gliomas. Children with medulloblastoma, ependymoma, atypical teratoid rhabdoid tumor and diffuse intrinsic pontine glioma often face challenges with overall survival both at diagnosis and at recurrence. Similar to high grade glioma, most of these tumors have no accepted standard of care at relapse/recurrence. Therefore, determining potential opportunities to improve outcomes for these children is pivotal.

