4. Patients with active bleeding are not eligible. Specifically, no clinically significant GI bleeding, GI perforation, intra-abdominal abscess or fistula for 6 months prior to enrollment, no hemoptysis or other signs of pulmonary hemorrhage for 3 months prior to enrollment.
5. Patients with evidence of an acute intracranial or intratumoral hemorrhage on CT or MRI are not eligible (patients with evidence of resolving hemorrhage will be eligible).
6. Major surgery within 28 days of enrollment. Complete wound healing from major or minor surgery must have occurred prior to enrollment. Minor surgery (including uncomplicated tooth extractions) within 7 days of enrollment. Subjects with clinically relevant ongoing complications from prior surgery are not eligible.
7. Concurrent uncontrolled hypertension defined as sustained blood pressure > 95th percentile for age, height and gender (systolic or diastolic) despite optimal antihypertensive treatment within 7 days of the first dose of study treatment.
8. Patients with any medical or surgical conditions that would interfere with gastrointestinal absorption of this oral agent are not eligible.
9. Infection: Patients who have an uncontrolled infection are not eligible.
10. Patients who have received a prior solid organ transplantation are not eligible.
11. Patients who in the opinion of the investigator may not be able to comply with the safety monitoring requirements of the study are not eligible.
12. Subjects who have received cabozantinib or have an allergy to cabozantinib are excluded. Subjects who have previously received tyrosine kinase inhibitors are allowed.
13. Subjects who have not received radiation therapy as part of their prior treatment are excluded.

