#### 14.6 Efficacy Analysis

The efficacy set will be used for all the efficacy analysis. For the primary efficacy aim of the disease control rate (CR, PR, or SD for at least 6 months), an estimate will be determined along with the corresponding exact 95% binomial confidence interval. A similar analysis will be done for the secondary objective of objective response rate (CR, PR).

For PFS and OS, the median and their corresponding two-sided 95% confidence intervals will be calculated using the Kaplan-Meier method. Estimates and 95% confidence intervals will also be provided for 6 and 12 months.

A listing of the patients who used corticosteroid will be provided.

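### Where all measurable disease was irradiated after the last documented progression, disease control cannot be attributed to cabozantinib, and the plan does not identify these patients

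*Combined protocol and SAP*

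**What the plan says.** Prior radiotherapy is compulsory. Exclusion 13 states: "Subjects who have not received radiation therapy as part of their prior treatment are excluded".

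Inclusion 7.a.iii gives three radiotherapy intervals:

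- "XRT: At least 14 days after local palliative XRT (small port";
- "At least 150 days must have elapsed if prior TBI, craniospinal XRT or if" half or more of the pelvis was irradiated;
- "At least 42 days must have elapsed if other substantial BM radiation".

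Focal cranial irradiation is not named, although Section 2 lists "focal irradiation to the tumor bed" as part of the usual approach to high grade glioma.

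On the disease to be measured, Inclusion 3 says "Disease Status: Patients must have measurable disease" and otherwise excludes only linear leptomeningeal enhancement without a mass. Section 13 and Appendix VII score change in all measurable enhancing lesions against baseline, with no rule for lesions irradiated shortly before entry.

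Section 14.6 sets the analysis: "For the primary efficacy aim of the disease control rate (CR, PR, or SD for at least 6 months" is estimated with an exact 95% binomial interval, ORR is handled similarly, and PFS and OS by Kaplan-Meier. Section 14.2 describes a single-arm pilot. No analysis takes account of time since radiotherapy.

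**The concern.** The intervals in 7.a.iii follow the type of field and the marrow exposed, not the effect of radiation on the tumour that will be measured. If all of a patient's measurable disease was irradiated for the current relapse, or if refractory disease is entered soon after irradiation, the baseline MRI is taken while that treatment may still be acting. Any later shrinkage or stability then has two possible causes, and a single arm offers no comparison to separate them. Post-radiation enlargement raises the same problem in reverse, because an increase of 25% or more is progression under Section 13.

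Disease control rate, ORR and PFS are affected. Section 17 says these results are the pilot response data requested before a larger trial would be considered, so what they can be attributed to is central to their use.

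**Working it through.** **1. Timing permitted by the text.** Section 7 puts the pre-study MRI within 14 days of starting drug. Footnote 1 of the study schedule puts eligibility studies within two weeks of enrolment. Scans done for clinical reasons before consent may serve as baseline. Inclusion 7.a.iii does not say whether its 14 days run to enrolment or to first dose.

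- If both windows run to the same day, the shortest gap from end of small-port irradiation to baseline MRI is 14 − 14 = 0 days.
- The first on-study MRI is at Day 28 of Cycle 3, that is 3 × 28 = 84 days after first dose (give or take a week).
- If the 14 days run to first dose, that scan falls 14 + 84 = 98 days after irradiation ended. Any radiation effect emerging over those 98 days is scored as change on cabozantinib.

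**2. Whether another rule removes these patients.**

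| Provision | Effect |
|---|---|
| Inclusion 2 (relapsed or refractory) | Does not require progression after the latest irradiation |
| Inclusion 4 (no standard therapy) | Silent on irradiation of the measured disease |
| Section 7.2 (no concurrent radiotherapy) | Applies on treatment, not before entry |
| Section 13 (independent radiologist) | Reads against the same baseline; cannot assign cause |
| Section 14.3.3 (no significant violations) | These patients are eligible, so they stay in |

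**3. The plan's own figure.** Section 14.4 gives the chance of seeing one or more events among 10 patients, 1 − (1 − p)^10. For p = 0.05, 0.10, 0.15, 0.20, 0.25 and 0.30 this is 0.401, 0.651, 0.803, 0.893, 0.944 and 0.972, which matches the printed table. The plan gives no null rate and no success threshold.

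**4. Weight of one patient.** Section 6 plans 11 patients, so one patient is 1/11 = 9.1 points (1/10 = 10 points at the size used in Section 14.4). Suppose, as an assumption, that the drug truly controls 2 of 11. Exact (Clopper-Pearson) 95% intervals are:

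| Scenario | Observed | Rate | Exact 95% interval |
|---|---|---|---|
| One drug-controlled patient scored PD because of post-radiation enlargement | 1/11 | 9.1% | 0.2 to 41.3% |
| No misattribution | 2/11 | 18.2% | 2.3 to 51.8% |
| One patient controlled by radiotherapy credited to the drug | 3/11 | 27.3% | 6.0 to 61.0% |

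**5. Upward component alone, illustrated.** Let f be the share of patients in the affected group and q the chance that radiotherapy alone gives six months' control. Both are assumptions; the documents give neither. With a wholly inactive drug, the chance of one or more apparent disease controls in 10 is 1 − (1 − fq)^10:

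- f = q = 0.1: 1 − 0.99^10 = 9.6%
- f = q = 0.3: 1 − 0.91^10 = 61%
- f = q = 0.5: 1 − 0.75^10 = 94%

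Without carry-over it would be 0. This ignores false progression, so it is not an estimate of net bias.

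**The case against.** The strongest case against is that few patients may be affected and that no stated decision turns on them.

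- **Reach.** A reader might infer from compulsory radiotherapy and the account of tumour-bed irradiation in Section 2 that most patients are exposed. The documents do not support that. Section 2 describes initial treatment, and Inclusion 2 admits patients in first to third relapse, so first-line irradiation ordinarily precedes the qualifying relapse. This objection stands and confines the point to re-irradiation at the current relapse, or refractory disease entered soon after irradiation.
- **Scoring.** Section 13 sums all measurable enhancing lesions and calls PD on progression of any lesion. One irradiated, stable lesion among several cannot by itself produce disease control. This also stands, and limits the point mainly to patients whose measurable disease was all irradiated.
- **Direction.** A reader might infer that the disease control rate is biased upward. Enlargement after radiation works the other way, although Section 13 softens it by letting doubtful cases continue under observation. The net sign is not established.
- **Decision.** The intervals in the working overlap heavily, and there is no go/no-go rule. That is true, but Section 17 gives the response data a purpose, and that purpose depends on attribution.
- **Existing latitude.** Section 14.1 allows further exploratory analysis. A split chosen after responses are known carries less weight than one fixed at baseline, and the study schedule does not call for the date and field of the last radiotherapy to be recorded.

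**Conclusion.** The point holds for a defined subset: patients whose measurable disease was all irradiated after the most recent documented progression. The plan admits them, does not identify them, and counts their CR, PR or six-month SD as cabozantinib disease control. In a single-arm trial that attribution cannot be made. Each misclassified patient moves the rate by 9.1 points at 11 patients, in either direction. The number of such patients is unknown and may be zero.

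Two further inferences should be resisted. The documents contain no figure for control after re-irradiation, so they do not show that radiotherapy contributes as much as the drug in these patients. Nor do they show that the 14-day interval is wrong as an eligibility rule. The gap is in attribution and reporting. It should be closed before on-study scans are read, but it does not undermine the trial as a whole.

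**What to change.** 1. **Baseline record.** Add the end date and field of the last radiotherapy.
2. **Flag.** Before any on-study MRI is read, flag each patient whose measurable disease was all irradiated with no documented progression of it afterwards. For refractory patients with no earlier documented progression, flag if all measurable disease lies in the last field and no later progression is shown. The flag is set per patient and fixed at baseline, so it cannot depend on outcome.
3. **Scoring.** Leave Section 13 unchanged, over all measurable lesions. Patients with both irradiated and non-irradiated disease then need no special rule, and response and progression are treated alike.
4. **Analysis.** In Section 14.6, report disease control rate, ORR and PFS with and without flagged patients, and state that attribution to the drug rests on the unflagged patients. Keep everyone in the safety and OS analyses.

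The cost is one baseline field, one extra analysis and a wider interval for the restricted estimate. If one of 11 patients is flagged and not controlled, an observed 1/11 (0.2 to 41.3%) becomes 1/10 (0.3 to 44.5%).

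One limit remains: transient enlargement recorded as progression before entry would leave a patient unflagged. The recorded date and field at least let a reader see such cases. Any change to the radiotherapy intervals themselves is for the investigators.
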